## 4.2 Exclusion criteria

- 1) current use of insulin therapy;
- 2) history of hypoglycemia unawareness, or severe hypoglycemia requiring assistance;
- 3) history of end-stage renal disease or renal dysfunction as evidenced by eGFR < 60 mL/min/1.73 m^2 by MDRD formula;
- 4) history of lactic acidosis or diabetic ketoacidosis;
- 5) active liver disease or elevated alanine transferase (ALT) levels  $\geq 2.5$  times upper limit of normal at the time of enrollment;
- 6) history of bladder cancer or undiagnosed hematuria;
- 7) history of breast cancer;
- 8) history of polycythemia;
- 9) evidence of volume depletion or hypotension (systolic blood pressure < 90 mmHg);
- 10) systolic blood pressure > 180 mmHg or diastolic blood pressure > 105 mmHg;
- 11) diagnosed cardiovascular disease (unless cleared for a moderate intensity exercise program by a specialist) including:
  - a. any history of acute coronary syndrome, hospitalization for unstable angina, myocardial infarction, or revascularization with coronary artery bypass grafting or percutaneous coronary intervention;
  - b. other evidence of coronary artery disease;
  - c. peripheral vascular disease, valvular heart disease, cardiomyopathy, aortic dissection, tachyarrhythmias, bradyarrhythmias, prior stroke or TIA;
  - d. prior hospitalization for heart failure; or
  - e. ECG findings concerning for ischemic heart disease (i.e. pathological Q-waves, ST-segment-T-wave abnormalities in contiguous leads, left anterior hemiblock, left bundle branch block, second or third degree atrioventricular block).
- 12) dependence on oxygen;
- 13) history of any disease requiring frequent intermittent or continuous systemic glucocorticoid treatment;
- 14) history of bariatric surgery, or planned bariatric surgery in the next 1.5 years;
- 15) history of any major illness with a life expectancy of < 3 years;
- 16) history of injury or any other condition that significantly limits participant's ability to achieve moderate levels of physical activity;
- 17) any history of excessive alcohol intake, acute or chronic;

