### **5.3.1.1 Treatment with and handling of Forxiga**

Participants randomized to the intervention group will be started on Forxiga 5 mg po daily for 4 days and then the dose will be increased to 10 mg po daily. Participants will be continued on this dose for 12 weeks. Forxiga will be manufactured and shipped by AstraZeneca. Labels will be prepared in accordance with Good Manufacturing Practice and local regulatory guidelines for labeling. The drug will be stored at room temperature (15-30°C) in accordance with the storage conditions specified on the package label. Creatinine will be checked 2 weeks after drug initiation, and then monthly during the intensive metabolic intervention. Forxiga will be permanently discontinued if eGFR falls to  $<60 \text{ mL/min/1.73m}^2$ . Forxiga contains lactose and may cause abdominal discomfort in lactose-intolerant individuals. Forxiga will be temporarily stopped or permanently discontinued if a participant develops side effects.

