## 6.3 Safety

### 6.3.1 Safety variables

Information on the following prespecified safety outcomes will be prospectively collected in all study participants during the trial:

- 1) Death (and cause of death as determined by a physician);
- 2) Non-fatal myocardial infarction or angina resulting in hospitalization or emergency room admission;
- 3) Non-fatal stroke or transient ischemic attack diagnosed by a physician;
- 4) Heart failure resulting in hospitalization or emergency room admission;
- 5) Resuscitated cardiac arrest or life-threatening arrhythmia (including documented or presumed ventricular fibrillation, sustained ventricular tachycardia, asystole, or pulseless electrical activity);
- 6) Cardiogenic shock diagnosed by a physician;
- 7) Diabetic ketoacidosis or hyperglycemic hyperosmolar state diagnosed by a physician;
- 8) Documented new fractures;
- 9) Newly diagnosed cancers;
- 10) Genitourinary infections diagnosed by a physician;
- 11) Moderate (eGFR 30-60 mL/min/1.73 m^2 by MDRD formula) or severe (eGFR <30 mL/min/1.73 m^2) renal dysfunction;
- 12) Symptomatic and severe hypoglycemic events (see below for definitions);
- 13) Hospital or emergency room admissions (and reasons for admission).

Participants will be asked to record all hypoglycemic episodes and symptoms in a diary that will be provided to them. Moreover, they will be explicitly asked about any episodes of symptomatic or severe hypoglycemia during every visit and telephone follow-up.

*Symptomatic hypoglycemia* is defined as an event with clinical symptoms consistent with hypoglycemia, based on data recorded in the participant's diary. These will be further categorized as confirmed (i.e. with a concomitant home glucose reading  $\leq 3.0$  mmol/L) or unconfirmed. Symptomatic hypoglycemic events and those that result in alteration of any of the study drugs will be recorded.

*Severe hypoglycemia* is defined as an event with clinical symptoms consistent with hypoglycemia in which the participant required the assistance of another person, and one of the following: (i) the event was associated with a documented self-measured or laboratory plasma glucose level  $\leq 2.0$  mmol/L; or (ii) the event was associated with prompt recovery after oral carbohydrate, intravenous glucose, or glucagon administration. Any episode of severe hypoglycemia will be recorded and reviewed within one working day.

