### **11.2 Statistical analyses**

All group comparisons will be conducted according to the intention-to-treat principle with inclusion of data from all participants according to their treatment group assignment, regardless of adherence to therapy. The primary outcome in this study is the proportion of patients in the intervention group who achieve drug-free diabetes remission 24 weeks after randomization compared to the control group. The treatment groups will be compared using a chi-squared test with  $\alpha = 0.05$  level of significance. The outcome will be reported as a risk difference in the induction of remission between the intervention group and the control group with 95% confidence interval. Any individual who withdraws/drops out prior to the 24, 36, 48 and 64 week visit will be classified as not having achieved drug-free diabetes remission at that point in time. Participants who fail to achieve remission or have hyperglycemia relapse will be censored with respect to diabetes remission outcomes.

For secondary analyses, a chi-squared test will be used for dichotomous outcomes and a two-sample t-test (or a non-parametric equivalent) for continuous outcomes. Secondary outcomes will be used only for generation of new hypotheses. Clinical and metabolic predictors of the successful induction of diabetes remission will be evaluated using logistic regression modeling. We do not plan to perform any interim analyses in this trial.

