### 13. APPENDIX A

**Table 1.** Schedule of visits and assessments in the intervention group (I), control group (C), and both groups (X).

	Weeks after randomization																			
	-1	0	0.5	1	1.5	2	2.5	3	3.5	4	4.5	5	5.5	6	7	8	9	10	11	12
Eligibility criteria	X																			
Informed consent	X																			
Randomization		X																		
Start study medications		I																		
Stop diabetes medications																				X
Clinic visit	X	X		I		I		I		I		I		X		I		I		X
Telephone follow-up			I		I		I		I		I		I		I		I		I	
Adherence to medications and side effects			I	I	I	I	I	I	I	I	I	I	I	X	I	I	I	I	I	X
Review SMBGs			I	I	I	I	I	I	I	I	I	I	I	X	I	I	I	I	I	X
Height	X																			
Weight	X	X						I						X		I		I		X
Waist and Hip Circumference		X												X						X
Blood pressure	X	X		I		I		I		I		I		X		I		I		X
Physical activity and food frequency questionnaires*	X																			X
ECG	X																			
Fasting serum for storage**	X																			
FPG	X																			
Serum ALT	X																			
Serum creatinine	X					I								I				I		
Urine BhCG***	X																			
HbA1C	X																			X
Two glucose profiles****														X						X
Return to standard glycemic care if hyperglycemia relapse identified																				
AE/SAE Review and Reporting			X	X	X	X	X	X	X	X	X	X	X	X	X	X	X	X	X	X

\*A quality of life questionnaire will also be administered at -1, 12 and 64 weeks.

\*\*Fasting serum sample will be taken for storage during the screening visit and at 16 weeks.

\*\*\*Urine BhCG will be measured in women with childbearing potential.

\*\*\*\* Two six-point glucose profiles will be collected on separate days. Each six-point glucose profile will include pre-meal and 2-hour post-meal SMBG readings taken on the same day.

	Weeks after randomization													
	12.5	16	20	24	28	32	36	40	44	48	52	56	60	64
Eligibility criteria														
Informed consent														
Randomization														
Start study medications														
Stop diabetes medications														
Clinic visit		X		X			X			X				X
Telephone follow-up	X		X		X	X		X	X		X	X	X	
Adherence to medications and side effects	X	X	X	X	X	X	X	X	X	X	X	X	X	X
Review SMBGs	X	X	X	X	X	X	X	X	X	X	X	X	X	X
Height														
Weight		X		X			X			X				X
Waist and Hip Circumference		X		X			X			X				X
Blood pressure		X		X			X			X				X
Physical activity and food frequency questionnaires*				X			X			X				X
ECG														
Fasting serum for storage**		X												

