FPG		X												
Serum ALT		X												X
Serum creatinine		X												X
Urine BhCG***														
HbA1C				X			X			X				X
Two glucose profiles****														
Return to standard glycemic care if hyperglycemia relapse identified	X	X	X	X	X	X	X	X	X	X	X	X	X	X
AE/SAE Review and Reporting	X	X	X	X	X	X	X	X	X	X	X	X	X	X

\*A quality of life questionnaire will also be administered at -1, 12 and 64 weeks.

\*\*Fasting serum sample will be taken for storage during the screening visit and at 16 weeks.

\*\*\*Urine BhCG will be measured in women with childbearing potential.

\*\*\*\* Two six-point glucose profiles will be collected on separate days. Each six-point glucose profile will include pre-meal and 2-hour post-meal SMBG readings taken on the same day.

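### The only renal outcome is an eGFR category in people who enter at 60 or more: it ignores the size of a fall, and its count is not comparable between arms because creatinine is drawn five times against two

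*Combined protocol and SAP*

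**What the plan says.** - **Outcome.** Section 6.3.1, item 11, lists renal dysfunction as a prespecified safety outcome in two grades: "Moderate (eGFR 30-60 mL/min/1.73 m 2 by MDRD formula", and severe, below 30. No other renal outcome appears.
- **Entry.** Section 4.2, criterion 3, excludes "renal dysfunction as evidenced by eGFR < 60 mL/min/1.73 m 2 by MDRD formula", so a value of exactly 60 is eligible.
- **Drug rule.** Section 5.3.1.1 uses the same number: "Forxiga will be permanently discontinued if eGFR falls to" below 60.
- **Measurement on drug.** The same section says "Creatinine will be checked 2 weeks after drug initiation, and then monthly during the intensive metabolic intervention". It describes the Forxiga arm only.
- **Schedule.** Appendix A, Table 1, is keyed as "Schedule of visits and assessments in the intervention group (I), control group (C), and both groups (X". Read by column, its creatinine row has both groups at screening, the intervention group alone at weeks 2, 6 and 10, and both groups at weeks 16 and 64.
- **Analysis.** Section 11.2 says that for secondary analyses "a chi-squared test will be used for dichotomous outcomes", with a t-test or equivalent for continuous outcomes. It names no eGFR or creatinine change and sets out no safety analysis.

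**The concern.** The protocol treats renal function as worth screening on, monitoring and stopping drug for, yet its one renal outcome records only which side of a fixed line a value lies on. A fall from 110 to 62 is no event, while a fall from 61 to 59 is one. The result therefore depends heavily on entry eGFR and on measurement noise near 60, and the screening value, which would separate these from a real change, is not used.

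The second fault is comparability. If item 11 counts anyone with a value below 60 during the trial, the intervention arm has more chances to be counted. The excess could be read as a renal effect of the course when part or all of it comes from the number of draws.

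At stake is the interpretation of renal safety for the regimen. The primary remission result is not affected.

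**Working it through.** The documents state no renal event rate, eGFR distribution, SD or renal power, so there is no figure of theirs to reproduce. All distributions below are assumptions. The documents supply 76 per arm, entry at 60 or more, and the draw schedule.

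**1. How many real falls stay out of the category?** Take entry eGFR as normal with mean m and SD s, truncated at 60, and a uniform fall d. The share going below 60 is

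[Φ((60+d−m)/s) − Φ((60−m)/s)] / [1 − Φ((60−m)/s)].

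With m = 90, s = 15, d = 5: (Φ(−1.67) − Φ(−2)) / (1 − Φ(−2)) = (0.0478 − 0.0228)/0.9772 = 2.6%, or 1.9 of 76 people. Over m = 80-100 and s = 12-20:

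| Fall | Go below 60 | Do not go below 60 |
|---|---|---|
| 5 units | 0.1-8.1% | 92-99.9% |
| 10 units | 0.6-17.8% | 82-99% |
| 15 units | 1.8-30.6% | 69-98% |
| 20 units | 4.7-47.5% | 53-95% |
| 30% of entry value | 11.7-66.7% | 33-88% |

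Most falls up to about 15 units are missed at every setting. For a 30% fall that is no longer assured.

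**2. Count of draws.** Intervention: weeks 2, 6, 10, 16, 64 = 5. Control: weeks 16, 64 = 2.

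**3. Effect of 5 draws against 2 with no drug effect.** Assume true eGFR with SD 15 and independent within-person noise of SD 5-8, and count anyone with any value below 60. At mean 90 and noise SD 5, 3.6% against 2.0% are counted: 0.036 × 76 = 2.7 people against 0.020 × 76 = 1.5, a ratio of 1.8. Across means 80-100 the ratio is about 1.8-1.9. If entry is instead decided by a noisy screening reading (mean 85-95), it is about 1.6-1.9, and an uncorrected chi-squared test on that count rejects in 2-19% of trials although nothing is happening.

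**4. What change from screening would add.** Simulation: true eGFR mean 85-95, SD 15, noise SD 5-8, noisy screening reading of at least 60, two-sided 0.05. The true fall in the intervention arm is 4 units.

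| Situation | Count below 60, chi-squared | ANCOVA on screening value |
|---|---|---|
| One common reading, whole fall present | 2-14% | 62-95% |
| Fall at weeks 2, 6, 10 only; any value on the real schedule | 11-46% | not possible at weeks 2-10 (no control draws) |
| Half the fall persists at week 16 | – | 19-44% |
| Fall reversed by week 16 | – | about 5% |

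The 11-46% is not usable power, because it includes the draw-count inflation of step 3.

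**5. What weeks 2, 6 and 10 can give.** The SD of a change is √2 × noise = 7.1 to 11.3. The 95% half-width is 1.99 × 7.1/√76 = 1.6 to 1.99 × 11.3/√76 = 2.6 units. The mean change in that arm is well estimated, but it has no control.

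**6. Boundary.** Exactly 60 is eligible under section 4.2 and does not meet the section 5.3.1.1 trigger, but it lies inside the 30-60 category of item 11.

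**The case against.** The other side has several sound points.

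- **Reporting.** A reader might infer that renal safety will be reported only as threshold crossings and dismissed on a non-significant chi-squared test. The documents do not say so. Section 6.3.1 lists what is collected, and the chi-squared rule in section 11.2 is written for secondary analyses, where renal function does not appear. The only stated safety objective, in section 2.3, is hypoglycemia.
- **Direction.** A reader might also infer that the count would hide a fall during the course. On the actual schedule the count leans the other way. For a 4-unit fall present only at weeks 2, 6 and 10 (mean 90, noise SD 5), about 4.5 intervention participants against 1.5 controls would be counted, part of it from the extra draws.
- **Power.** The 62-95% for ANCOVA does not apply to a fall confined to the drug course. The common post-baseline visits are weeks 16 and 64, and week 16 is about 4 weeks after the 12-week course ends.
- **Other routes.** Monthly investigator review (6.3.1), dose-changing adverse events (6.3.3.1), serious adverse events (6.3.3.2) and admissions (6.3.1, item 13) could bring a marked fall to light.
- **Proportion.** The trial calls itself a pilot, and the creatinine values will exist whatever the plan says.

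All of this limits the claim. What remains is that no defined outcome or planned analysis captures a silent fall that stays at or above 60 and changes no dose, and nothing in the plan handles the unequal draws.

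**Conclusion.** The point holds as a gap in outcome definition and analysis. Three facts come straight from the documents: the only renal outcome is a fixed category, everyone enters at 60 or more, and no analysis uses the screening value or the size of a fall. The five-against-two schedule is also explicit, so a raw between-arm count below 60 is biased towards more intervention events, by about 1.6-1.9 times under the assumptions above.

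The sizes depend on assumed eGFR means, SDs and independent within-person noise. The ANCOVA figures also require the fall to be present at the visit analysed. Neither arm-level method can isolate Forxiga during the course: the intervention combines Forxiga, metformin, glargine and lifestyle therapy, and controls have no draws at weeks 2, 6 or 10. This is a safety-reporting improvement worth making. It does not show that a renal effect would be concealed.

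**What to change.** In sections 6.3.1 and 11.2:

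1. Keep item 11 as a categorical listing. Limit any between-arm comparison of it to weeks 16 and 64, and state the unequal creatinine schedule.
2. Reconcile sections 4.2 and 6.3.1 on a value of exactly 60.
3. Add change in eGFR from screening at weeks 16 and 64, compared between arms by ANCOVA with the screening value as covariate and a 95% CI. Describe it as a post-course effect that cannot show a fall reversed after drugs stop.
4. Add mean change with 95% CI at weeks 2, 6 and 10 in the intervention arm, labelled as uncontrolled change during the combined intervention and not attributed to Forxiga.

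The cost is a few SAP lines. Every creatinine value is already scheduled, so no draw or visit is added, and no treatment or discontinuation rule is touched. The remaining weakness is that the drug course has no concurrent renal control.

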**Secondary research questions:**

- 1) Compared to the control group, does this therapeutic approach achieve drug-free diabetes remission in a higher proportion of patients than standard diabetes therapy at 36, 48 and 64 weeks after randomization?
- 2) Compared to the control group, does this therapeutic approach achieve drug-free HbA1C <6.0% in a higher proportion of patients than standard diabetes therapy at 24, 36, 48 and 64 weeks after randomization?
- 3) Compared to the control group, does this therapeutic approach achieve drug-free diabetes regression in a higher proportion of patients than standard diabetes therapy at 24, 36, 48 and 64 weeks after randomization? Diabetes regression is defined as HbA1C 6.5-6.9% off glucose-lowering agents for at least 12 weeks.
- 4) What HbA1C levels are achieved in the intervention group and the control group at 12, 24, 36, 48 and 64 weeks after randomization?
- 5) What rates of hypoglycemia are observed in the intervention group and the control group during 64 weeks of follow-up?
- 6) What is the change in weight, body mass index (BMI), waist circumference and waist/hip ratio from baseline to 12, 24, 36, 48 and 64 weeks in the intervention group and the control group?
- 7) Are age, gender, ethnicity, diabetes duration, smoking, family history of diabetes, baseline BMI, waist circumference, HbA1C or fasting plasma glucose (FPG) determinants of diabetes remission at 24 weeks after randomization?

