## **2.3 Safety objective**

To determine rates of severe and non-severe hypoglycemic episodes in the treatment groups during 64 weeks of follow-up.

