#### **5.3.1.4 Monitoring during the induction phase of the trial**

At the first study visit, intervention group participants will be taught how to self-monitor capillary blood glucose and how to inject insulin. Participants and their families will also be taught how to recognize and treat hypoglycemia. During the intensive metabolic intervention, participants will be asked to monitor glucose at least twice daily at varying times, including before and 2 hours after meals, and during exercise. Research staff will meet with intervention group participants once a week during the first 6 weeks of the trial and will contact them by telephone at least once a week between visits to review glucose readings, medication titration, medication adherence and side effects (see schedule in Table 1 in Appendix A). Research staff will continue to meet with intervention group participants every 2 weeks and will contact them by telephone every other week during week 7-12 of the trial. All hypoglycemic episodes will be documented and reviewed with an investigator promptly. Glucose-lowering therapy will be adjusted accordingly.

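### Hypoglycemia is asked about at 18 contacts in the intervention arm and 2 in controls during weeks 0.5-12, so the 64-week rates carry differential ascertainment in the induction phase, mainly for symptomatic events

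*Combined protocol and SAP*

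**What the plan says.** Section 2.3 states the only safety objective: "To determine rates of severe and non-severe hypoglycemic episodes in the treatment groups during 64 weeks of follow-up". Secondary research question 5 in Section 1.2 asks: "What rates of hypoglycemia are observed in the intervention group and the control group during 64 weeks of follow-up". Neither names a between-arm test.

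Section 6.3.1 gives two routes for finding events. One is a diary: "Participants will be asked to record all hypoglycemic episodes and symptoms in a diary that will be provided to them". The other is direct questioning, in that "they will be explicitly asked about any episodes of symptomatic or severe hypoglycemia during every visit and telephone follow-up". Symptomatic hypoglycemia is defined as "based on data recorded in the participant's diary" and is confirmed if a concomitant home reading is 3.0 mmol/L or less. Severe hypoglycemia requires another person's help.

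The contact schedules differ. Section 5.3.1.4 has staff meet intervention participants "once a week during the first 6 weeks of the trial and will contact them by telephone at least once a week between visits", then alternate visits and calls in weeks 7-12. In the same section "participants will be asked to monitor glucose at least twice daily at varying times". For controls in this phase, Section 5.3.2 describes an opening meeting and sets no self-testing frequency. Table 1 adds control visits at weeks 6 and 12, with glucose profiles at both.

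The Table 1 row "AE/SAE Review and Reporting" is marked X (both groups) in every column from week 0.5 to 64. Section 11.2 has no analysis specific to hypoglycemia and does not mention the unequal schedule.

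**The concern.** A symptomatic episode enters the data if the participant writes it down, or remembers it when asked. In the induction phase one arm is prompted once or twice a week and the other every six weeks. The trial is open label for participants and staff (Section 5.2.1), so nothing masks the difference. Testing differs too: an arm told to test at least twice daily may have a meter reading to hand more often when symptoms occur, so more of its events can be classed as confirmed.

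The imbalance falls in the same 12 weeks in which the intervention arm is titrating insulin glargine. In that phase a higher rate in the intervention arm could come from treatment, from closer questioning and testing, or from both, and the planned data do not separate them. A single 64-week figure per arm hides this by pooling the unequal phase with an equal one.

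Table 1 has a separate inconsistency. It marks adverse-event review for both groups at weeks when controls have no visit or call, and the plan does not say how that review is done.

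**Working it through.** **Contacts, counted from Table 1** (I = intervention only, X = both; the week 0 visit, common to both arms, is left out)

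| Period | Intervention | Control |
|---|---|---|
| Clinic, weeks 0.5-12 | 1, 2, 3, 4, 5, 6, 8, 10, 12 = 9 | 6, 12 = 2 |
| Telephone, weeks 0.5-12 | 0.5, 1.5, 2.5, 3.5, 4.5, 5.5, 7, 9, 11 = 9 | 0 |
| Total, weeks 0.5-12 | 18 | 2 |
| Weeks 12.5-64 (5 visits + 9 calls) | 14 | 14 |
| Total, weeks 0.5-64 | 32 | 16 |

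Section 5.3.1.4 gives the same 18: 6 visits + 6 calls, then 3 visits + 3 calls. The ratio is 9:1 in induction and 2:1 over the whole study.

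**Adverse-event row.** It is marked X in all 18 columns from 0.5 to 12. Controls have contact in 2 of these, so 18 - 2 = 16 columns have no control contact (0.5, 1, 1.5, 2, 2.5, 3, 3.5, 4, 4.5, 5, 5.5, 7, 8, 9, 10, 11).

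**Illustration of size.** The documents give no reporting rates, so everything here is assumed: equal true rates in both arms, a chance of reporting that halves every h weeks until the next contact, and no help from the diary. With k = ln 2 / h, the share captured in an interval of L weeks is f(L) = (1 - exp(-kL)) / (kL). Captured weeks are the sum of L × f(L):

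- Intervention, weeks 0-12 (12 intervals of 0.5 week, 6 of 1 week): A = 6 f(0.5) + 6 f(1)
- Control, weeks 0-12 (2 intervals of 6 weeks): B = 12 f(6)
- Either arm, weeks 12-64 (intervals of 0.5, 3.5 and twelve of 4 weeks): M = 0.5 f(0.5) + 3.5 f(3.5) + 48 f(4)

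| h (weeks) | A | B | M | Weeks 0-12: A/B | 64 weeks: (A+M)/(B+M) | 64 weeks, five-fold induction rate in both arms: (5A+M)/(5B+M) |
|---|---|---|---|---|---|---|
| 4 | 11.26 | 7.46 | 37.73 | 1.51 | 1.08 | 1.25 |
| 8 | 11.62 | 9.36 | 44.07 | 1.24 | 1.04 | 1.12 |
| 12 | 11.74 | 10.14 | 46.52 | 1.16 | 1.03 | 1.08 |

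Example for h = 4: f(0.5) = 0.958, f(1) = 0.918 and f(6) = 0.622. So A = 6 × (0.958 + 0.918) = 11.26, B = 12 × 0.622 = 7.46, and A/B = 1.51.

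The 64-week ratio is smaller because 52 of the 64 weeks have identical contacts. It rises when events cluster in induction.

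**The case against.** A reader might infer that the 64-week safety objective is confounded outright. The documents do not go that far, for five reasons.

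- Questioning is not the only route. The diary is offered to participants without distinction by arm, the definition of symptomatic hypoglycemia rests on it, and questioning comes on top. This stands, and it makes the ratios above upper-end illustrations as far as recall is concerned. It does not remove the concern: the protocol does not say how or when diaries are collected, and a diary discussed up to twice a week is likely to be kept better than one first seen at week 6 (a judgement).
- The imbalance covers 12 of 64 weeks. This stands, and the 64-week ratios reflect it.
- Severe events need another person's help and can qualify on prompt recovery alone, so they are less likely to go unreported. Unconfirmed symptomatic events are counted too, and controls use the same glucometers. The testing difference therefore bears mainly on the confirmed/unconfirmed split.
- No pooled between-arm test is specified. It is tempting to say that Section 11.2 would compare hypoglycemia by t-test. It does not assign hypoglycemia to any method, and it treats secondary outcomes as hypothesis-generating. Still, rates shown by arm will be compared.
- Under-capture in controls raises the apparent intervention/control ratio, so it would not hide harm from the intervention. This is fair as to direction, but the comparison could still be misstated.

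The adverse-event row may be meant as continuous reporting, since its label covers reporting as well as review. That is possible, but the table does not say so.

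**Conclusion.** The concern holds in limited form. The 18 versus 2 contact count and the 16 unsupported control entries are exact. It follows that hypoglycemia is ascertained unequally by design in weeks 0-12. The effect falls mainly on symptomatic events, is partly offset by the diary, and is weaker for severe events.

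The size cannot be determined from the documents. Under assumed half-lives of 4 to 12 weeks and no diary effect, equal true rates would show ratios of about 1.16-1.51 in weeks 0-12 and 1.03-1.08 over 64 weeks, or 1.08-1.25 over 64 weeks if the induction rate is five times higher in both arms. The model covers recall only and gives no estimate for the testing difference.

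A reader might also infer that weeks 12-64, with equal contacts, could serve as the fair safety comparison. They cannot replace the induction phase: Section 5.3.3 stops glucose-lowering drugs at the end of week 12 in participants with HbA1C below 7.3%, so the later period does not measure risk under the intensive regimen.

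**What to change.** - **Section 11.2.** Report hypoglycemia per person-time separately for weeks 0-12 and 12-64, with severe, confirmed symptomatic and unconfirmed symptomatic events shown separately. State that the between-arm contrast for symptomatic events in weeks 0-12 reflects unequal questioning and testing as well as treatment. Do not present weeks 12-64 as a substitute for induction-phase risk.
- **Section 6.3.1.** State that diaries are collected and reviewed in both arms at the shared week-6 and week-12 visits. This gives a common source but does not equalise prompting, because the intervention arm will already have been asked 11 times before week 6 (5 visits and 6 calls).
- **Table 1.** Reconcile the adverse-event row with the clinic and telephone rows at the 16 time points without control contact, and say how control events are gathered there. Do not simply re-mark those cells as intervention only. That would cut adverse-event review in controls, against Section 6.3.1 (prospective collection in all participants) and Section 6.3.5 (observation from consent to study end).

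The cost is analysis wording, a diary instruction at existing visits and a table correction; no extra visits are needed. The downside is a narrower claim for the induction-phase comparison between arms.
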